The age, gender, smoking history, diagnosis, length of mechanical ventilator use, APACHE II will be recorded. The pulmonary performance, including tidal volume, maximal inspiratory pressure (MIP), cough function, peak inspiratory pressure (PIP), positive end-expiratory pressure (PEEP), lung compliance, airway resistance, blood gas analysis, Barthel index, serum albumin, creatinine, electrolytes will record before, during (twice per week) and after intervention. We also follow the outcome of hospitalization, including the weaning rate, mortality, length of mechanical ventilator use, length of ICU stay and total length of hospitalization. We will further evaluate the diaphragm movement. Ultrasound was performed at the end of exhalation (without stimulation) to measure the thickness of the diaphragm, twice per week of participation, and then weekly until RCC discharge. All measurements were taken from muscles on the right-hand side of the participant by the same assessor at all assessment sessions. For the diaphragm, the probe was placed parallel to the anterior axillary line in the intercostal space between the 9th and 10th rib and moved in the cranial and caudal directions until the pleural line was identified. From this point, the probe was moved approximately 1 or 2 intercostal spaces lower to identify the costal diaphragm in the zone of apposition. In all measurements, the probe was placed perpendicular to the skin. We will analyze the diaphragm movement, thickness and the correlation with successful weaning rate.

Concomitant Treatments : 不適用

1. Concomitant Therapy :

2. Prohibited Therapy :

Statistical Methods :

1. Main study Hypothesis : Equality Superiority Non-inferiority
 Equivalence Other _____

2. Estimated Sample Size : 100_

3. Efficacy assessment group : Intent-to-treat (ITT) Per-Protocol (PP)
 Other _____

ITT: We include all eligible patients who meet the criteria had signed informed consents to participate this study.

4. Interim analysis : Yes No

Statistical methods : Categorical variables were described using counts (percentages).
 Parametric data were expressed as means \pm standard deviation (SD). Among the group

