2.5 Regulatory

This study will be conducted in compliance with the protocol approved by the Institutional Review Board, and according to Good Clinical Practice standards. No deviation from the protocol will be implemented without the prior review and approval of the IRB except where

it may be necessary to eliminate an immediate hazard to a research subject. In such case, the deviation will be reported to the IRB as soon as possible.

3. Objectives and Endpoints

3.1 Study Objectives:

3.1.1 Primary objective:

To evaluate the benefit of high protein supplementation and core muscle rehabilitation and trunk NMES intervention in weaning from ventilator

3.1.2 Secondary objectives:

The impact of renal function and digestion status after high protein intake
The benefit in nutrition status and diaphragm weakness and the correlation to weaning status

3.1.3 Other exploratory objectives (if any):

1.2 Study endpoints:

3.2.1 Primary endpoint:

Weaning rate

(weaning success defined as weaning from ventilator for 5 consecutive days)

3.2.2 Secondary endpoints:

In hospital mortality, Length of mechanical ventilator usage,
Length of ICU stay and total length of hospitalization,
Serum albumin level improvement, Creatinine clearance rate

3.2.3 Other exploratory endpoints (if any):

4. Study Design

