The age, gender, smoking history, diagnosis, length of mechanical ventilator use, APACHE II will be recorded. The pulmonary performance, including tidal volume, maximal inspiratory pressure (MIP), cough function, peak inspiratory pressure (PIP), positive end-expiratory pressure (PEEP), lung compliance, airway resistance, blood gas analysis, Barthel index, serum albumin, creatinine, electrolytes will record before, during (twice per week) and after intervention. We also follow the outcome of hospitalization, including the weaning rate, mortality, length of mechanical ventilator use, length of ICU stay and total length of hospitalization. We will further evaluate the diaphragm movement. Ultrasound was performed at the end of exhalation (without stimulation) to measure the thickness of the diaphragm, twice per week of participation, and then weekly until RCC discharge. All measurements were taken from muscles on the right-hand side of the participant by the same assessor at all assessment sessions. For the diaphragm, the probe was placed parallel to the anterior axillary line in the intercostal space between the 9th and 10th rib and moved in the cranial and caudal directions until the pleural line was identified. From this point, the probe was moved approximately 1 or 2 intercostal spaces lower to identify the costal diaphragm in the zone of apposition. In all measurements, the probe was placed perpendicular to the skin. We will analyze the diaphragm movement, thickness and the correlation with successful weaning rate.

Flow Chart :

Abbreviation: RCC, respiratory care center; PMV, prolonged mechanical ventilation; NM, neuromuscular; DVT, deep vein thrombosis; CHF, congestive heart failure; BMI, body mass index; TV, tidal volume; MIP, maximal inspiratory pressure; PIP, peak inspiratory pressure; PEEP, positive end-expiratory pressure; UC, usual care; HP, high protein, NMES, neuromuscular electrical stimulation

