4.3 Schedule of Activities

Time-Event scheme :

Phase	Screening	Treatment	4±1	6~7	Treatment	8~10	11±1	Treatment	13~14	Treatment	15~17	18±1	Treatment	20~21	Follow-up	22~27	28±1	
Day	0-1	1~3	4±1	6~7	8~10	11±1	13~14	15~17	18±1	20~21	22~27	28±1						
In-hospital visit	X	X	X		X	X		X	X	X	X	X	X	X	X	X	X	
Screening/Administrative/Safety																		
ICF/assent form	X																	
Inclusion/Exclusion criteria	X																	
Medical and surgical history, demographics	X																	
Physical exam	X		X				X				X				X			
Vital signs	X	X	X				X				X			X		X		
Height and body weight	X		X				X				X			X		X		
Pulmonary performance (ventilator)	X		X				X				X			X		X		
Laboratory study	X		X				X				X			X		X		
Barthel index	X																	
Echo for diaphragm evaluation	X		X				X				X			X		X		
Randomization/Administration																		
Randomization	X																	
Administration of high protein diet	X	X	X	X	X	X	X	X	X	X	X	X	X	X				
Administration of core muscle rehabilitation	X	X		X	X		X		X		X		X					
Administration of NMES	X	X		X	X		X		X		X		X					
Efficacy/Safety																		
Weaning profile	X		X				X				X	X	X	X		X		
Creatinine clearance rate	X		X				X				X	X	X	X		X		
Weaning rate													X	X				
Length of mechanical ventilator use													X	X		X		
Length of ICU stay													X	X		X		
Length of hospitalization													X	X		X		
In hospital Mortality													X	X				

5. Study Population

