11.2 Planned Statistical methods of analysis

Categorical variables were expressed as count and percentage. Parametric data were expressed as mean \pm standard deviation (SD). A Student's t-test was used to compare parametric data. Fisher's exact test was used to compare non-parametric data. We used a receiver operating characteristic (ROC) curve to identify the optimal cut-off-value for the maximum multiplication of sensitivity and specificity. Logistic regression was used for multivariate analysis. Kaplan–Meier survival analysis was performed to assess weaning and survival outcomes. Statistical significance was set at a p-value < 0.05 . Statistical analyses were performed using GraphPad Prism version 8 (GraphPad Software, La Jolla, CA, USA) and IBM SPSS Statistics 26 (SPSS, Chicago, IL, USA).

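### Section 11.2 picks an ROC cut-off from the trial data with no internal validation, and the diaphragm–weaning correlation is not limited to scans taken before weaning

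*Combined protocol and SAP*

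**What the plan says.** Section 11.2 says that an ROC curve will identify the "optimal cut-off-value for the maximum multiplication of sensitivity and specificity". The next sentence says "Logistic regression was used for multivariate analysis". Neither sentence names a predictor, an outcome or a measurement time. No hold-out set, cross-validation or bootstrap is mentioned in section 11 or in the Synopsis.

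The ultrasound text is in the Synopsis (Study Procedures) and again in 4.1. Scans are taken "twice per week of participation, and then weekly until RCC discharge", and the analysis is given in one sentence: "We will analyze the diaphragm movement, thickness and the correlation with successful weaning rate". The schedule in 4.3 has a row "Echo for diaphragm evaluation" that begins at screening, so a pre-treatment scan exists.

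This analysis serves a secondary objective (3.1.2): "The benefit in nutrition status and diaphragm weakness and the correlation to weaning status". The outcome is fixed in 3.2.1: "weaning success defined as weaning from ventilator for 5 consecutive days".

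Section 4.1 lists twelve other ventilator, functional and laboratory measures that could act as markers. These "will record before, during (twice per week) and after intervention".

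**The concern.** There are two separate weaknesses.

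The first is optimism. A cut-off that maximises a criterion in one sample fits that sample's noise as well as its signal. Sensitivity and specificity read off at that point in the same patients are therefore biased upward, and a clinician who applied the cut-off to new patients should expect worse performance. If the marker is itself picked as the best of several, the bias grows.

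The second is timing. If a scan taken once the patient is breathing unassisted enters the correlation, the association may run from weaning to the diaphragm. The protocol's own background (the part on ventilator-induced diaphragm dysfunction) says that an inactive diaphragm wastes quickly and that spontaneous effort limits this. By that reasoning ventilation status alters the measurement, and a thicker or more mobile diaphragm in weaned patients could be a result of weaning.

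**Working it through.** **Sample size.** Section 11.1 gives 10 patients in usual care and 30 in each of three other arms: 10 + 3 × 30 = 100, which reproduces the stated total. Section 4.2 gives 80 and 100 with 20% dropout. Since 80 / (1 − 0.20) = 100, the usable number is 80 to 100. The Synopsis omits cases with missing data, so the lower figure is realistic.

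**Assumptions.** The documents give no weaning rate, AUC, sensitivity or specificity. I assumed weaning of 30%, 50% or 70% and a true AUC of 0.50, 0.65 or 0.75.

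**Method.** One normally distributed marker with unit SD in each group; mean difference d = √2 × Φ⁻¹(AUC). In each simulated data set:
- choose the cut-off c that maximises sensitivity × specificity;
- record the apparent J = sensitivity + specificity − 1 in that sample;
- compute the true J at the same c, which is Φ(c) − Φ(c − d).

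There were 3,000 data sets per setting.

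| n | weaned | AUC | apparent J | true J | excess |
|---|---|---|---|---|---|
| 100 | 50% | 0.50 | 0.080 | 0.000 | 0.080 |
| 100 | 50% | 0.65 | 0.285 | 0.208 | 0.077 |
| 100 | 50% | 0.75 | 0.430 | 0.356 | 0.074 |
| 100 | 30% | 0.65 | 0.294 | 0.207 | 0.087 |
| 80 | 30% | 0.50 | 0.102 | 0.000 | 0.102 |
| 80 | 30% | 0.65 | 0.304 | 0.205 | 0.099 |
| 80 | 30% | 0.75 | 0.447 | 0.353 | 0.094 |

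Over all 18 settings the excess runs from 0.074 to 0.102. Divided between the two measures, that averages 0.074 / 2 = 3.7 to 0.102 / 2 = 5.1 percentage points each on sensitivity and specificity.

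**Several candidate markers.** With n = 100, 50% weaned, independent candidates that all have AUC 0.65, and the best one kept (1,000 data sets):
- best of 5: 0.383 against 0.209, excess 0.174;
- best of 10: 0.417 against 0.210, excess 0.207.

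Real candidates are correlated, so the excess would fall somewhere between these values and the single-marker result.

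**Scan timing.** No arithmetic from the documents applies, so the passages have to be set side by side. Scans are twice weekly during participation, on average every 7 / 2 = 3.5 days. Success needs five consecutive days off the ventilator. If twice-weekly scanning is still under way when a patient weans, at least one scan will normally fall inside the period that defines success, and the weekly scans that follow come later still. The sentence announcing the correlation excludes none of these.

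To see whether a size could be attached, I took a marker with no predictive value and tested change to day 21 against weaning by day 21 (n = 100, 50% weaned by day 21, exponential weaning times). Every input to the diaphragm's response was assumed. With a gain of 0.1 SD per week after weaning, the test was significant in 9% to 36% of trials as the SD of the change went from 1.4 down to 0.5. With 0.2 SD per week it was 20% to 89%. The nominal rate is 5%. The direction is consistent, but the spread is too wide to support a figure.

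**The case against.** The strongest reply is that much of this fills silence with the worst reading. Four parts of it stand.

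- A reader might infer that the plan relates weaning to scans taken during and after weaning. The documents do not say so. They state when scans are acquired, not which are analysed, and a screening scan is available. The defect is an unspecified time point.
- A reader might also infer that ultrasound is the ROC marker. Section 11.2 names no marker, and 4.1 offers a dozen others. The two weaknesses should be kept apart.
- Choosing a cut-off does not inflate the AUC of a single pre-named marker. Optimism affects the AUC only if markers are selected or combined.
- Confining predictors to baseline or the first days would discard later pre-weaning scans, which bear on a secondary objective about benefit in diaphragm weakness during treatment.

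Two further replies carry less weight. Section 11.1 calls the research exploratory, but does so to justify the sample size. The correlation is a listed secondary objective, the exploratory-objectives field (3.1.3) is blank, and p < 0.05 is applied without marking the cut-off as hypothesis-generating. It is also true that the plan does not promise to report accuracy for new patients. But a cut-off described as optimal on sensitivity and specificity will be read with those two figures beside it.

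**Conclusion.** The point holds in two limited parts.

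First, following 11.2 as written gives optimistic sensitivity and specificity at the chosen cut-off. For one pre-named marker the excess on sensitivity + specificity − 1 is about 0.07 to 0.10, given the assumed weaning rates and AUCs and a normally distributed marker. It is larger if the best of several markers is kept.

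Second, nothing keeps post-weaning scans out of the diaphragm–weaning correlation, so reverse causation is possible. Its size cannot be derived from the documents, and I claim none.

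This is a minor, worthwhile improvement to secondary analyses. The primary comparison of weaning between arms does not depend on it.

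**What to change.** Amend 11.2 as follows.

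- Name the marker or markers, the outcome and the measurement time for the ROC and logistic analyses.
- Report sensitivity and specificity at the chosen cut-off with bootstrap optimism correction, repeating the cut-off search and any marker selection in every resample, with 95% confidence intervals.
- Report the AUC with a confidence interval, and correct it only if markers are selected or combined.
- For the diaphragm–weaning association, use the screening scan or scans at fixed landmark days. At each landmark include only patients still ventilated, relate the scan to later weaning, and adjust for arm. Using several landmarks keeps the later pre-weaning scans in the analysis.
- Treat scans taken after weaning as descriptive.

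The cost is a few lines of text and a little more coding, with no extra measurements. The reported accuracy will be lower, and later landmarks will have fewer patients.

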comparisons, one-way analysis of variance (ANOVA) followed by Dunnett's test, where appropriate, was used to determine the statistical significance of the difference between means. The follow-up parametric data were compared using the paired student's t-test. Non-parametric data were determined by chi-squared tests. Analyses of primary and secondary outcomes are performed with the use of time-to-event methods according to the intention-to-treat principle. All analyses were two-sided, and $p<0.05$ was considered statistically significant. Statistical analyses were performed using Prism version 5 (GraphPad Software Inc., La Jolla, CA, USA).

5. Handling of Missing Data :

Omit the cases with missing data and analyze the remaining data.

2. Introduction and Rationale

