6.2. Concomitant Therapy

Not Applicable

7. Efficacy Assessments

The age, gender, smoking history, diagnosis, length of mechanical ventilator use, APACHE II will be recorded initially.

The pulmonary performance, including tidal volume, maximal inspiratory pressure (MIP), cough function, peak inspiratory pressure (PIP), positive end-expiratory pressure (PEEP), lung compliance, airway resistance, blood gas analysis, Barthel index, serum albumin, creatinine, electrolytes will record before, during (twice per week) and after intervention.

We also follow the outcome of hospitalization, including the weaning rate, mortality, length of mechanical ventilator use, length of ICU stay and total length of hospitalization.

8. Safety Assessments

We will follow serum creatinine level and creatinine clearance rate weekly.

During core muscle rehabilitation and NMES, vital signs (heart rate, blood pressure, respiratory rate) and parameters in ventilator (tidal volume, FiO₂, peak airway pressure) will be monitored.

9. Adverse event reporting

We will report SAEs to the IRB of Chang Gung Medical Foundation according to the Serious Adverse Event Reporting Procedures and Guidelines as posted in the Clinical Trials Resource on the website of Chang Gung Medical Foundation IRB. SAE reports to the IRB should include the following information when calling the Medical Monitor:

- *Date and time of the SAE*
- *Date and time of the SAE report*
- *Name of reporter*
- *Call back phone number*
- *Affiliation/Institution conducting the study*
- *Protocol number*
- *Title of protocol*
- *Description of the SAE, including attribution to drug and expectedness*

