11.1 Sample size Determination

This is an exploratory research, we determine the enrolled number according to the

number of patients admitted to RCC annually.

Ten patients will be assigned to UC group.

Thirty patients will be included in another 3 group.

A total 100 patients will be enrolled.

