11.2.1 Efficacy analysis

Kaplan–Meier survival analysis was performed to assess weaning and survival outcomes.

Mann Whitney test was used for compare non-parametric data (weaning rate, length of ventilator use, length of ICU stay and length of hospitalization).

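### Every weaning test in the plan is unadjusted and its one logistic model is unspecified, although three plausible baseline covariates are already collected

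*Combined protocol and SAP*

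**What the plan says.** The primary endpoint is binary: "weaning success defined as weaning from ventilator for 5 consecutive days" (section 3.2.1). The definition gives no day by which weaning is judged.

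Several methods could apply to it:
- Section 11.2 says of Fisher's test that the "exact test was used to compare non-parametric data".
- The synopsis (Statistical methods) gives chi-squared for the same kind of data, and time-to-event methods by intention to treat for primary and secondary outcomes.
- Section 11.2.1 names weaning rate explicitly: "Mann Whitney test was used for compare non-parametric data (weaning rate, length of ventilator use". It also plans Kaplan-Meier for weaning. No Cox model or stratified test appears.
- Section 11.2 adds "Logistic regression was used for multivariate analysis", directly after a sentence on ROC cut-offs. Section 11.2.1 does not mention this model.

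Baseline data: section 7 has "length of mechanical ventilator use, APACHE II will be recorded initially", and lists MIP among the measurements taken before, during and after the intervention. The synopsis speaks of stratifying patients into the four groups but names no factor.

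Size and level: "Ten patients will be assigned to UC group" (section 11.1), with 30 in each other group and 100 in total, on feasibility grounds. "Statistical significance was set at a p-value < 0.05" (section 11.2).

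**The concern.** The efficacy comparison, as written, makes no use of three baseline measurements that could plausibly predict weaning. Nothing in the randomisation as described balances them either. With so small a control arm, a sizeable difference between groups on one of them is a real possibility, and the plan has no declared way to allow for it.

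The logistic model could do this, but its place beside the ROC sentence leaves open that it is a predictor model rather than a treatment comparison. If it is used for treatment, its covariates can be picked after the results are seen. What is at stake is precision, protection against chance imbalance, and a weaning result that does not depend on which of several tests is reported.

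**Working it through.** **1. Inputs.** From section 11.1: arms of 10, 30, 30 and 30. The stated total reproduces: 10 + 3 × 30 = 100. The plan states no power, effect size or weaning rate, so there is no power figure to reproduce. Level: two-sided 0.05. Weaning rates and covariate strengths below are assumptions.

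**2. Chance imbalance (needs no assumed rate).** For a standardised covariate, the SD of the difference in means is sqrt(1/n1 + 1/n2).
- 10 v 30: sqrt(1/10 + 1/30) = 0.365; 0.5/0.365 = 1.369; two-sided normal tail = 17.1%.
- 30 v 30: sqrt(2/30) = 0.258; 0.5/0.258 = 1.936; tail = 5.3%.
- If the 20% loss in section 4.2 fell evenly (8 v 24): SD 0.408, tail 22.1%.
- At least one of three independent covariates, 10 v 30: 1 − (1 − 0.171)³ = 43%.

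How much this moves the result depends on prognostic strength. The conditions assumed were no treatment effect, 50% weaning, one covariate, and an imbalance above 0.5 SD favouring the 30-patient arm. The unadjusted risk difference then shifts on average by about 5, 9 and 13 points at odds ratios per SD of 1.35, 1.82 and 2.46.

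**3. What adjustment adds.** Simulation, 4,000 trials per scenario, three independent normal covariates of equal strength. The 10 v 30 contrast (group 4 v usual care) comes from one 100-patient model with assumed rates of 40, 50, 60 and 70%. Its power is corrected to a true 5% size. The 30 v 30 column assumes 40% v 70% and compares chi-squared with the adjusted likelihood-ratio test. It is not size-corrected (sizes 4.8–5.5% and 5.6–6.8%).

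| Odds ratio per SD | Joint AUC | 10 v 30, unadjusted → adjusted | Gain | 30 v 30, chi-squared → adjusted | Gain |
|---|---|---|---|---|---|
| 1.00 | 0.50 | 36.5% → 36.5% | 0 | 66.4% → 67.1% | 1 |
| 1.35 | 0.64 | 37.1% → 38.0% | 1 | 66.3% → 68.5% | 2 |
| 1.82 | 0.75 | 36.0% → 42.5% | 6 | 65.6% → 74.5% | 9 |
| 2.46 | 0.82 | 35.8% → 49.4% | 14 | 66.7% → 81.1% | 14 |

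**4. What Fisher's test costs, separately.** Exact rejection probability = sum over all (a, b) of Bin(a; n1, p1) × Bin(b; n2, p2) × 1[p-value ≤ 0.05]. Size is maximised over a common rate; power is at an assumed 45% v 78%.

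| Contrast | Fisher: maximum size | Fisher: power | Uncorrected chi-squared: maximum size | Uncorrected chi-squared: power |
|---|---|---|---|---|
| 10 v 30 | 2.85% | 39.7% | 5.4% | 50.6% |
| 30 v 30 | 2.74% | 67.2% | 5.5% | 76.1% |

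On a 0/1 outcome, the normal-approximation Mann-Whitney test has the same power as chi-squared.

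**5. Putting the two together.** At the same assumed rates, a four-arm Firth model (1,500 simulated trials per setting, covariate AUC assumed 0.70 to 0.77) gave power of 50–54% for 10 v 30 and 77–81% for 30 v 30. Against chi-squared (51% and 76%), adjustment itself accounts for roughly 0–3 and 1–5 points. The rest of the gap from Fisher is the change of test.

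**6. Size of the adjusted test.** Ordinary logistic likelihood-ratio test, pairwise 10 v 30 with three covariates: 7.1–7.9%. Pooled 100-patient model: 6.0–6.7%. Firth in the pooled model: 3.9–5.3%.

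**The case against.** The strongest reply has five parts.

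- *The plan already contains an adjusted model.* True, and a reader might wrongly infer that it has none. The defect is that the model's outcome, treatment term, covariates and role are unstated, so it does not protect the weaning comparison.
- *Randomisation already makes the unadjusted test valid.* This stands. A reader might infer that the unadjusted analysis is biased, or that imbalance is to be expected on any given factor. Neither follows: 17% per factor is a minority of trials, and over repeated trials the cost is precision.
- *The power gain is speculative.* Largely stands. The documents give no weaning rate or prognostic strength, and MIP (below 30 mmHg) and ventilator days (more than 21) are both range-restricted by eligibility, which may weaken them. A reader who set Fisher directly against an adjusted model might credit the whole gap to adjustment; step 5 shows most of it comes from leaving Fisher. Fisher is also not the test section 11.2.1 ties to weaning.
- *Too few events for six terms.* Partly stands. At 50% weaning there are about 50 events. If usual care weans at 45% and the other arms at 78%, only 10 × 0.55 + 90 × 0.22 = 25 patients fail to wean, about 4 per term. That favours a short fixed covariate list and penalised fitting; it does not rule the model out.
- *The trial is exploratory and limited by 10 controls.* The second half stands. The first explains the sample size, but the plan still applies a 0.05 threshold to a named primary endpoint.

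**Conclusion.** The point holds as a choice of method that can be improved at low cost. All the weaning tests are unadjusted, the one model that could adjust is unspecified, no stratification factor is named, and the covariates are already recorded. The 17% and 5% imbalance figures rest only on the arm sizes and a normal approximation; Fisher's maximum size is exact.

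The benefit of adjustment is assumption-dependent, from nil with weak covariates to about 14 points of power with strong ones. The Fisher loss of about 9 to 11 points at 45% v 78% is a separate matter and arises only if Fisher is the test used.

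Neither change rescues the comparison with usual care. Unadjusted 10 v 30 power is 19% to 46% across the assumed pairs 40/60, 50/70, 30/60, 40/70 and 50/80%. At 40% v 70%, even very strong covariates lift it only to about 49% at a true 5% size in the four-arm model. A reader might infer that adjustment could stand in for a larger control arm; these figures do not support that.

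**What to change.** In section 11.2.1, name one primary weaning analysis and align the synopsis and section 11.2 with it:
- One logistic model over all four randomised arms. The outcome is weaning success by a stated day, which the endpoint definition must then also give.
- Terms: treatment group, plus baseline prior ventilator days, APACHE II and MIP, continuous and fixed in advance.
- Fitting by Firth penalised likelihood, because the ordinary pairwise 10 v 30 test runs at 7 to 8%.
- Results as standardised risk differences with 95% confidence intervals.
- A simple imputation rule for missing baseline covariates, so that no randomised patient is dropped. The synopsis and section 11.4 now remove incomplete cases, so adding covariates under that rule could shrink the analysed set.
- The unadjusted comparison and the Kaplan-Meier/time-to-event analysis kept as supportive and labelled so. If the logistic sentence in section 11.2 was meant for a predictor model, say so and keep it apart.

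Cost: wording, with no new data collection. Firth fitting may need software beyond the packages named, the covariates must be fixed before results are seen, and the gain may be small if they prove weakly prognostic.

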5.3 Withdrawal criteria

1. Return to ICU for unstable vital sign or any necessity of surgery.
2. Patient refuse further intervention
3. Physicians judge the patients' condition are not suitable for further intervention.

10. Treatments

6.1.Treatment Administration

1. High protein diet:

The HP groups will maintain unchanged total daily caloric intake and increasing protein content to 1.5g/kg/day. The specific formulas were chosen for their different energy and protein requirement (mainly Nutri-Aid , or NU-PEP HN , according to patients' digestion, and may add Whey-Aid if necessary (above formula are available in CGMH currently)).

We will maintain the nutrition strategies for 21 days according to patients' weaning condition. Protein provision was not reduced in case of renal failure.

2. Core muscle rehabilitation:

Sitting on bedside with or without aids, for 30 minutes, twice per day, 5 days per week, for 3 weeks.

3. Neuromuscular electrical stimulation (NMES):

NMES was applied for 30 min, twice per day, 5 days per week, for 3 weeks, via surface rectangular electrodes. Electrodes were placed on back designed to activate latissimus dorsi and abdominal wall designed to activate the transversus abdominis and internal and external oblique muscles as previously McCaughey et al described ³⁷. Electrical muscle stimulation was performed by using a commercial stimulator (GEMORE, GM300E, Taipei, Taiwan) with biphasic waves at a simulation frequency of 30 Hz and pulse width of 400s, cycling 2s on and 4s off. Electrical muscle stimulation intensity was gradually increased until a visible muscle contraction was observed (median 60 mA [range 50–65 mA].

The subjects in the control group received similar electrode placement and intervention duration, except that the stimulator power was off.

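### In-hospital death is to be analysed by Kaplan–Meier with no rule for live discharge; if discharge is censored, the risk is overstated, and by more in the arm that discharges more patients

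*Combined protocol and SAP*

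**What the plan says.** - **Endpoint.** Section 3.2.2 opens its list of secondary endpoints with "In hospital mortality, Length of mechanical ventilator usage". The synopsis gives the same list. No death endpoint that counts deaths in any location, or deaths by a fixed day, appears.
- **Follow-up.** Section 4.1 says "We also follow the outcome of hospitalization, including the weaning rate, mortality", so mortality is followed as part of the hospital stay. The schedule in section 4.3 carries a row for "In hospital Mortality", labels its visits as in-hospital and ends at day 28±1. It lists no contact after discharge.
- **Method.** Section 11.2 says "Kaplan–Meier survival analysis was performed to assess weaning and survival outcomes", and section 11.2.1 repeats it. The statistical methods in the synopsis are broader: "Analyses of primary and secondary outcomes are performed with the use of time-to-event methods according to the intention-to-treat principle".
- **Other tests.** Fisher's exact test (section 11.2) and chi-squared tests (synopsis) are listed in general terms, but neither is assigned to mortality. Section 11.2.1 names the outcomes for the Mann–Whitney test, and mortality is not one of them.
- **Silent.** No time origin, horizon, censoring rule, treatment of live discharge or competing-risk method is given. The missing-data rule in the synopsis, "Omit the cases with missing data and analyze the remaining data", does not settle it, because a patient discharged alive has a complete in-hospital outcome.

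**The concern.** A patient who leaves hospital alive can no longer die in hospital. Live discharge therefore competes with the endpoint; it is not a loss to follow-up. If it is treated as censoring, Kaplan–Meier estimates what mortality would be if nobody were ever discharged and those who left had the same death hazard as those who stayed. That is not the in-hospital mortality the plan names, and it exceeds it whenever deaths occur after discharges have begun.

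The interventions are meant to speed weaning, and length of stay is itself an endpoint, so different discharge rates between arms are a foreseeable result of success. The overstatement would then differ by arm. An arm that discharges more patients could look worse than it is, or a real advantage in in-hospital death could disappear from the curves. In a trial that section 11.1 calls exploratory, the reported percentages and curves are a main product.

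**Working it through.** **Inputs.** Section 11.1 gives 10 usual-care patients and 30 in each of three other arms: 10 + 3 × 30 = 100, the stated total. Significance is at 0.05, two-sided. The plan gives no death or discharge rate, so every rate below is an assumption. The horizon is 28 days, the last scheduled visit.

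**1. One 30-patient arm, 6 deaths.** Deaths fall on days 4, 8, 12, 16, 20 and 24. Live discharges are spread evenly from day 7.5 to day 21.5 and censored. Crude in-hospital death is 6/30 = 20% throughout.

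| Live discharges | At risk at each death | 1 − Kaplan–Meier |
|---|---|---|
| 0 | 30, 29, 28, 27, 26, 25 | 20.0% |
| 5 | 30, 28, 26, 24, 22, 20 | 22.1% |
| 10 | 30, 28, 25, 21, 17, 15 | 25.1% |
| 15 | 30, 28, 23, 18, 13, 10 | 30.0% |
| 18 | 30, 28, 22, 16, 10, 7 | 35.7% |

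Last row: 1 − (29/30)(27/28)(21/22)(15/16)(9/10)(6/7) = 0.357.

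**2. Discharge unrelated to prognosis.** Take death hazard h = 0.01/day in both arms and discharge hazard a.
- 1 − Kaplan–Meier = 1 − exp(−28h) = 24.4%, whatever a is.
- In-hospital death = h/(h + a) × [1 − exp(−28(h + a))], which is 21.4% at a = 0.01 and 13.6% at a = 0.05.
- Overstatement: 24.4 − 21.4 = 3.0 points v 24.4 − 13.6 = 10.8 points. The curves coincide although in-hospital death differs by 21.4 − 13.6 = 7.8 points.

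**3. Discharge related to prognosis.** Each arm mixes frail patients (proportion p, death hazard hf) with robust patients (death hazard hr). Only robust patients are discharged, at hazard a, and discharge does not change their death hazard. The Kaplan–Meier curve follows the average death hazard among those still in hospital:

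λ(t) = [p·hf·exp(−hf·t) + (1 − p)·hr·exp(−(hr + a)t)] / [p·exp(−hf·t) + (1 − p)·exp(−(hr + a)t)],

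and 1 − Kaplan–Meier = 1 − exp(−∫λ dt) from 0 to 28. The two arms differ only in a (0.01 v 0.05/day).

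| p, hf, hr | True 28-day mortality, both arms | In-hospital death | 1 − Kaplan–Meier | False gap |
|---|---|---|---|---|
| 0.3, 0.03, 0.003 | 22.7% | 22.0% v 20.1% | 24.1% v 30.6% | 6.5 points |
| 0.4, 0.03, 0.002 | 26.0% | 25.6% v 24.5% | 27.7% v 34.9% | 7.2 points |
| 0.3, 0.02, 0.005 | 22.0% | 20.9% v 17.9% | 22.9% v 26.9% | 4.0 points |

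In the first mixture the overstatement of in-hospital death is 24.1 − 22.0 = 2.1 points v 30.6 − 20.1 = 10.5 points. The order of the arms reverses in all three mixtures.

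**4. Log-rank test.** The first mixture was simulated 4,000 times per setting with no true difference in mortality and a = 0.01 v 0.05. With discharge censored, the two-sided rejection rate is 7.7% for 30 v 30 (7.0% against the faster-discharging arm) and 4.7% for 10 v 30. With vital status known to day 28 in everyone it is 5.3% and 4.6%. The simulation standard error near 5% is √(0.05 × 0.95/4000) ≈ 0.3 points.

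**The case against.** **The censoring is inferred.** No section says that discharged patients are censored. If they were carried event-free to a fixed day, or if day-28 status were obtained, the overstatement would not arise. That stands: the documents leave the handling open, and do not state a wrong rule. But with no post-discharge follow-up described, censoring at discharge is the default reading of a Kaplan–Meier plan.

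**The direction is not automatic.** A reader might infer that the arm discharging more patients must look more lethal. The documents do not support that. It needs discharge to be linked to prognosis, which is plausible here but not documented. Step 2 shows that with equal hazards and unrelated discharge the curves are equal.

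**A larger figure is easy to construct.** Suppose two arms each have 25% in-hospital deaths, with 65% v 45% discharged alive under constant hazards. The cumulative death hazard is −ln(1 − 0.25 − 0.65) × 0.25/0.90 = 0.640 v −ln(1 − 0.25 − 0.45) × 0.25/0.70 = 0.430, so Kaplan–Meier reads 47.3% v 34.9%. That 12-point gap should not be taken as the size of the bias against an effective arm. The example gives the faster-discharging arm a death hazard 0.640/0.430 = 1.49 times as high, and contains no prognosis-linked discharge.

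**Part of the remedy is already there.** Counts, percentages, Fisher's exact test and an all-randomised population (section 11.3) are in the plan. They would serve, but they are not assigned to mortality, and the synopsis points secondary outcomes to time-to-event methods.

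**Conclusion.** The concern holds as a mismatch between endpoint and method, together with a missing rule. If discharge is censored, one minus Kaplan–Meier overstates in-hospital death, and in the scenarios worked it does so by more in the arm that discharges more patients. That arm can look worse than it is when discharge follows prognosis; on the assumed rates the false gap is about 4 to 7 points. When discharge is unrelated to prognosis, the harm is instead that a real difference in in-hospital death is hidden.

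The damage is to reported curves and percentages more than to tests. Log-rank error rises modestly for 30 v 30 and not meaningfully for 10 v 30. All sizes rest on assumed death and discharge rates and on censoring at discharge. The endpoint is secondary in an exploratory trial and the primary endpoint is unaffected, so this should be corrected but does not threaten the main conclusion.

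**What to change.** 1. In sections 11.2 and 11.2.1, limit the Kaplan–Meier sentence so that it does not cover in-hospital death, and bring the time-to-event sentence in the synopsis into line.
2. Report in-hospital death as a proportion of all randomised patients per arm, with a 95% confidence interval and Fisher's exact test. Alternatively, report cumulative incidence with live discharge as a competing event.
3. State the time origin and horizon, and state that patients are not censored at discharge. Patients withdrawn under section 5.3 stay in the denominator.
4. Use a Kaplan–Meier survival curve only to a fixed day, such as day 28, on which vital status is obtained for everyone regardless of location.

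Items 1 to 3 are changes of wording and use outcomes the plan already collects. Item 4 needs one small extra data item, because the plan describes no vital-status check after discharge.
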